12 SOURCE DOCUMENTS AND ACCESS TO SOURCE DATA/DOCUMENTS

The clinical site will maintain appropriate medical and research records for this trial, in compliance with ICH E6 GCP, Section 4.9, and regulatory and institutional requirements for the protection of confidentiality of subjects. The PI and clinical site will permit trial-related monitoring, audits, IRB review, and regulatory inspections as requested by FDA, DMID/NIAID, Emergent or their designee, including direct access to source data/documents (e.g., original medical records, laboratory reports, hospital documents, progress reports, signed ICFs in addition to eCRF's).

The data captured in source documents is transcribed into eCRFs by the study coordinator/staff. From this perspective, source documents are considered as origin for eCRF data and are subject to verification by the study monitor. Additional source data are all information, original records of clinical findings, observations, or other activities in a clinical trial necessary for the reconstruction and evaluation of the trial. Examples of these original documents and data records include, but are not limited to, hospital records, clinical and office charts, laboratory notes, memoranda, pharmacy dispensing records, recorded data from automated instruments, copies or transcriptions certified after verification as being accurate and complete and subject files and records kept at the pharmacy, laboratories, and medico-technical departments involved in the clinical trial.

13 QUALITY CONTROL AND QUALITY ASSURANCE

Processes outlined in the DMID-approved Master Clinical Quality Management Plan (CQMP) will be implemented by the clinical site, [REDACTED] Phase 1 Unit, to ensure the integrity of the clinical data, safety and welfare of human subjects, and that the clinical trial is conducted in accordance with the approved protocol and with the applicable federal regulations and ICH guidelines. Findings from the CQMP activities will be submitted by written report to Emergent within five business days.

Emergent will audit the clinical site as needed during the course of the study.

14 ETHICS/PROTECTION OF HUMAN SUBJECTS

14.1 Ethical Standard

The PI will ensure that this study is conducted in full conformity with the principles set forth in The Belmont Report: Ethical Principles and Guidelines for the Protection of Human Subjects of Research of the US National Commission for the Protection of Human Subjects of Biomedical and Behavioral Research (April 18, 1979) and codified in 45 CFR Part 46 and/or the ICH E6; 62 Federal Regulations 25691 (1997).

14.2 Institutional Review Board

██████████ IRB holds a current US Federal-wide Assurance issued by the Office of Human Research Protections.

Prior to initiation of the study, the site PI will submit the study protocol, sample ICF, and any other documents that pertain to subject information, recruitment materials such as advertisements, to IRB. The site PI must also submit any other information that may be requested to the IRB for review and approval. The site PI will request that the IRB provide written approval of the study and will keep on file records of approval of all documents pertaining to this study. A letter confirming the approval must be forwarded to the CRA prior to initiation of this study. This letter will be forwarded to Emergent and DMID prior to the initiation of the study.

The PI must submit and, where necessary, obtain approval from the IRB for all subsequent protocol amendments and changes to the ICF. The PI should notify the IRB of deviations from the protocol or SAEs occurring at the site, as well as other AE reports received from the ██████████ in accordance with local procedures.

The PI will be responsible for obtaining annual IRB approval or renewal throughout the duration of the study.

14.3 Informed Consent Process

Informed consent is a process that is initiated prior to the individual's agreeing to participate in the study and continuing throughout the individual's study participation. Extensive discussion of risks of this therapy will be provided to the subjects. Consent forms describing in detail the study products, study procedures, and risks are given to the subject and written documentation of informed consent is required prior to administering study product. Consent forms will be IRB-approved and the subject will be asked to read and review the document. Upon reviewing the document, the PI will explain the research study to the subject and answer any questions that may arise. The subjects will sign the informed consent document prior to any procedures being done specifically for the study. The subjects should have the

opportunity to think about the study and discuss with others prior to agreeing to participate. The subjects may withdraw consent at any time throughout the course of the study. A copy of the ICF will be given to the subjects for their records. The rights and welfare of the subjects will be protected according to 21 CFR 312.60.

14.4 Exclusion of Women, Minorities, and Children (Special Populations)

Children under age 18 years will be excluded from participation because insufficient data are available in adults to judge potential risk in children, and as a Phase 1 trial in healthy individuals, there is no known benefit. For these same reasons, this trial will not include other special classes of subjects, such as fetuses, neonates, prisoners, institutionalized individuals, or others who may be considered vulnerable populations.

Neither women nor minorities will be excluded from participation in this study. Women of child bearing potential may be included as per the inclusion criteria ([Section 5.1](#)). Subjects will be recruited without regard to gender or race. It is expected that race will reflect that within the community but that exclusion of women of child bearing potential may lead to disproportional numbers of males.

14.5 Subject Confidentiality

Subject confidentiality is strictly held in trust by the PI, his/her staff, and the Sponsor(s) and their agents. This confidentiality is extended to cover testing of biological samples and genetic tests in addition to the clinical information relating to participating subjects.

The study protocol, documentation, data, and all other information generated will be held in strict confidence. No information concerning the study or the data will be released to any unauthorized third party without prior written approval of the Sponsor.

The study monitor or other authorized representatives of the Sponsor may inspect all documents and records required to be maintained by the PI, including but not limited to, medical records (office, clinic, or hospital) and pharmacy records for the subjects in this study. The clinical study site will permit access to such records.

14.6 Study Discontinuation

The NIAID/DMID has the right to terminate/discontinue this study or an individual site's participation at any time. Reasons for terminating the study may include, but are not limited to, the following:

- Incidence or severity of adverse events indicates a potential health hazard;
- Data recording is inaccurate or incomplete;
- Investigator does not adhere to the protocol or applicable regulatory guidelines in conducting the study.

In the event that the study is discontinued, no further subjects will be dosed with UV-4B.

14.7 Future Use of Stored Specimens

Any plasma, blood, or urine left after all clinical laboratory testing is done will be discarded. Any plasma left after PK analysis will be stored at Emergent or designee bioanalytical laboratory and used for future research. A separately collected blood sample will be stored at Emergent or designated bioanalytical laboratory [REDACTED]

[REDACTED] At the completion of the protocol, the disposition of samples and data will be per Emergent instructions. Any loss or unanticipated destruction of samples or data will be reported to the IRB. In compliance with subject confidentiality and privacy act (e.g. HIPAA); no genetic testing, including pharmacogenomics, will be done on any stored specimens.

15 DATA HANDLING AND RECORD KEEPING

15.1 Data Management Responsibilities

Any source documents and laboratory reports must be reviewed by the clinical team and data management staff, who will ensure their accuracy and completeness. AEs must be graded based on the FDA Guidance for Industry: *Toxicity Grading Scale for Healthy Adult and Adolescent Volunteers Enrolled in Preventive Vaccine Clinical Trials* September 2007, as modified for this study and as appropriate for the administration of UV-4B

([Appendix II](#)).

Electronic data capture is the responsibility of the clinical trial staff at the site under the supervision of the site PI. During the study, the PI must maintain complete and accurate documentation for the study.

15.2 Data Capture Methods

Clinical data (including AEs and concomitant medications) will be entered into Medidata Rave, a 21 CFR Part 11-compliant electronic data capture (EDC) system managed by [REDACTED]. The EDC system access is password protected. Access is granted to specific individuals based on the roles identified for the study. Clinical study sites enter the data into EDC and [REDACTED] monitors the data entry and accuracy of data entered. Data are validated through a query resolution process, comprising both automated and manual queries.

15.3 Types of Data

Data for this study will include all data for safety and PK deemed necessary for the analysis per the protocol, demographic data, concomitant medication, AE and medical history. Externally collected data are received and processed to present a complete dataset reconciled with data collected in the EDC.

15.4 Timing/Reports

Data collected at the bedside are available for review once it is entered into the EDC. Data are collected, reviewed, and queries are issued by [REDACTED] data management. The CRA will monitor the data and may also create queries for site clarification. AE data and concomitant medication data are coded by the MedDRA® and World Health Organization Drug (WHO DD) dictionaries respectively. Details regarding data collection, review, reconciliation, and reporting are discussed in the Data Management Plan.

15.5 Study Records Retention

Study documents should be retained for a minimum of 2 years after the last approval of a marketing application in an ICH region, and until there are no pending or contemplated marketing applications in an ICH region, or at least 2 years have elapsed since the formal discontinuation of clinical development of the investigational product. These documents should be retained for a longer period, however, if required by local regulations. No records will be destroyed without the written consent of Emergent. It is the responsibility of Emergent to inform the PI when these documents no longer need to be retained.

15.6 Protocol Deviations

A protocol deviation is any noncompliance with the clinical trial protocol, GCP, or manual of procedures requirements. The noncompliance may be either on the part of the subject, the PI, or the study site staff. As a result of deviations, corrective actions and preventive actions are to be developed and documented by the site and implemented promptly with associated records provided to Emergent.

These practices are consistent with ICH E6:

- 4.5 Compliance with Protocol, Sections 4.5.1, 4.5.2, and 4.5.3;
- 5.1 Quality Assurance and Quality Control, Section 5.1.1
- 5.20 Noncompliance, Sections 5.20.1 and 5.20.2.

It is the responsibility of the site to identify and report deviations within 5 working days of identification of the protocol deviation, or within 5 working days of the scheduled protocol required activity. All deviations must be promptly reported in writing to Emergent.

16 PUBLICATION POLICY

The data generated by this study are confidential information of the Sponsor. The Sponsor will make the results of the study publicly available as stipulated per the National Institute of Health Public Access Policy implements Division G, Title II, Section 218 of PL 110-161 (Consolidated Appropriations Act, 2008) which states:

SEC. 218. The Director of the National Institutes of Health shall require that all investigators funded by the NIH submit or have submitted for them to the National Library of Medicine's Pub Med Central an electronic version of their final, peer-reviewed manuscripts upon acceptance for publication, to be made publicly available no later than 12 months after the official date of publication: Provided, that the NIH shall implement the public access policy in a manner consistent with copyright law.

By signing the study protocol, the PI agrees that the results of the study may be used for the purposes of national and international registration, publication, and information for medical and pharmaceutical professionals by the Sponsor. If necessary, the authorities will be notified of the PI's name, address, qualifications, and extent of involvement.

If the PI or [REDACTED] is to be included as an author of a publication manuscript prepared by the Sponsor, the Sponsor will allow the PI or [REDACTED] 60 days for full review of the manuscript before publication.

APPENDIX I SUBJECT FLOWDOWN

APPENDIX II UV-4B TOXICITY GRADING CRITERIA FOR NORMAL HUMAN SUBJECTS

Vital Signs*	Mild (Grade 1)	Moderate (Grade 2)	Severe (Grade 3)	Potentially Life Threatening (Grade 4)
Fever (°C)** (°F)**	38.0 – 38.4 100.4 – 101.1	38.5 – 38.9 101.2 – 102.0	39.0 – 40 102.1 – 104	>40 >104
Tachycardia – (beats per minute)	101 – 115	116 – 130	>130	Emergency room visit or hospitalization for arrhythmia
Bradycardia – (beats per minute)	50-54 if baseline >60	45-49 if baseline >60	<45 if baseline >60	Emergency room visit or hospitalization for arrhythmia
	45-50 if baseline ≤ 60	40-44 if baseline ≤ 60	<40 if baseline ≤ 60	
Hypertension (systolic) – mmHg	141 – 150	151 – 155	>155	Emergency room visit or hospitalization for malignant hypertension
Hypertension (diastolic) – mmHg	91 – 95	96 – 100	>100	Emergency room visit or hospitalization for malignant hypertension
Hypotension (systolic) – mmHg	85 – 89	80 – 84	<80	Emergency room visit or hospitalization for hypotensive shock
Respiratory Rate – breaths per minute	17-20	21-25	>25	Intubation

AE = adverse event; CRF = case report form
 * Subject should be at rest for all vital sign measurements.
 **Oral temperature; no recent hot or cold beverages or smoking
 All graded values representing a change from baseline must be reported as AEs. For clinical or laboratory observations not addressed by the toxicity grading criteria, Grade 0 = absent will be used in the AE CRF to indicate the toxicity grading criteria do not apply.

Systemic (General)	Mild (Grade 1)	Moderate (Grade 2)	Severe (Grade 3)	Potentially Life Threatening (Grade 4)
Nausea/vomiting	No to mild interference with activity or 1 to 2 episodes/24 hours	Moderate interference with activity or >2 episodes/24 hours	Prevents daily activity, requires outpatient IV hydration	Emergency room visit or hospitalization for hypotensive shock
Diarrhea	2 - 4 loose stools or < 400 gm/24 hours	5-6 stools or 400 – 800 gm/24 hours	7 or more watery stools or > 800gms/24 hours or requires outpatient IV hydration	Emergency room visit or hospitalization
Headache	No interference with activity	Repeated use of non-narcotic pain reliever > 24 hours or some interference with activity	Significant; any use of narcotic pain reliever or prevents daily activity	Emergency room visit or hospitalization
Fatigue	No interference with activity	Some interference with activity	Significant; prevents daily activity	Emergency room visit or hospitalization
Myalgia	No interference with activity	Some interference with activity	Significant; prevents daily activity	Emergency room visit or hospitalization

AE = adverse event; CRF = case report form
 
All graded values representing a change from baseline must be reported as AEs. For clinical or laboratory observations not addressed by the toxicity grading criteria, Grade 0 = absent will be used in the AE CRF to indicate the toxicity grading criteria do not apply.
				

Systemic (General)	Mild (Grade 1)	Moderate (Grade 2)	Severe (Grade 3)	Potentially Life Threatening (Grade 4)
Illness or clinical AE (as defined according to applicable regulations)	No interference with activity	Some interference with activity, not requiring medical intervention	Prevents daily activity and requires medical intervention	Emergency room visit or hospitalization

AE = adverse event; CRF = case report form
 
All graded values representing a change from baseline must be reported as AEs. For clinical or laboratory observations not addressed by the toxicity grading criteria, Grade 0 = absent will be used in the AE CRF to indicate the toxicity grading criteria do not apply.
				

Serum	Mild (Grade 1)	Moderate (Grade 2)	Severe (Grade 3)	Potentially Life Threatening (Grade 4)
Sodium – hyponatremia mEq/L	132 – 134	130 – 131	125 – 129	<125
Sodium – hypernatremia mEq/L	148 – 150	151 – 153	>154	Associated with seizures
Potassium – hyperkalemia mEq/L	5.3 – 5.4	5.5 – 5.6	>5.6	Associated with ECG changes
Potassium – hypokalemia mEq/L	3.0 – 3.5	2.5 – 2.9	2.0 – 2.4	≤1.9
Glucose – hypoglycemia mg/dL	65 – 69	55 – 64	45 – 54	<45
Glucose – hyperglycemia fasting mg/dL random mg/dL	100 – 110 111 – 125	111 – 125 126 – 200	>125 >200	Insulin requirements or hyperosmolar coma
Blood urea nitrogen increase mg/dL	21 – 26	27 – 31	>31	Requires dialysis
Creatinine increase mg/dL	1.5 – 1.7	1.8 – 2.0	2.1 – 2.5	>2.5 or requires dialysis
Calcium – hypocalcemia mg/dL	8.0 – 8.8	7.5 – 7.9	7.0 – 7.4	<7.0
Calcium – hypercalcemia mg/dL	10.6 – 11.0	11.1 – 11.5	11.6 – 12.0	>12.0
Magnesium – hypomagnesemia mg/dL	1.3 – 1.7	1.1 – 1.2	0.9 – 1.0	<0.9
Phosphorous – hypophosphatemia mg/dL	2.3 – 2.5	2.0 – 2.2	1.6 – 1.9	<1.6
Creatine phosphokinase – increase by factor	2.0 – 5.0 x ULN	5.1 – 10.0 x ULN	10.1 – 20 x ULN	>20 x ULN
Albumin – hypoalbuminemia g/dL	2.8 – 3.3	2.5 – 2.7	<2.5	--
Total protein – hypoproteinemia g/dL	5.5 – 5.9	5.0 – 5.4	<5.0	--
Alkaline phosphate – increase by factor	2.0 – 2.9 x ULN	3.0 – 5.0 x ULN	>5.0 – 10.0 x ULN	>10.0 x ULN
Liver function tests – ALT, AST increase by factor	1.1 – 2.5 x ULN	2.6 – 5.0 x ULN	5.1 – 10 x ULN	>10 x ULN
Bilirubin – when accompanied by any increase in liver function test increase by factor	1.1 – 1.25 x ULN	1.26 – 1.5 x ULN	1.51 – 1.75 x ULN	>1.75 x ULN

Serum	Mild (Grade 1)	Moderate (Grade 2)	Severe (Grade 3)	Potentially Life Threatening (Grade 4)
Bilirubin – when liver function test is normal; increase by factor	1.1 – 1.5 x ULN	1.6 – 2.0 x ULN	2.1 – 3.0 x ULN	>3.0 x ULN
Cholesterol increase mg/dL	201 – 210	211 – 225	>226	--
Pancreatic enzymes – amylase, and lipase – increase by factor	1.5 – 2.0 x ULN	2.1 – 3.0 x ULN	3.1 – 5.0 x ULN	>5.0 x ULN
AE = adverse event; ALT = alanine aminotransferase; AST = aspartate aminotransferase; CRF = case report form; ECG = electrocardiogram; ULN = upper limit of normal Criteria are modified for this study based on reference values. All graded values representing a change from baseline must be reported as AEs. For clinical or laboratory observations not addressed by the toxicity grading criteria, Grade 0 = absent will be used in the AE CRF to indicate the toxicity grading criteria do not apply.				

Hematology	Mild (Grade 1)	Moderate (Grade 2)	Severe (Grade 3)	Potentially Life Threatening (Grade 4)
Hemoglobin (Female) decrease - gm/dL	10.5-11.5	9.5-10.4	8.0 – 9.4	< 8.0
Hemoglobin (Female) change from baseline value - gm/dL	Any decrease – 1.5	1.6 – 2.0	2.1 – 5.0	> 5.0
Hemoglobin (Male) decrease - gm/dL	12.5 – 13.5	10.5 – 12.4	8.5 – 10.4	< 8.5
Hemoglobin (Male) change from baseline value – gm/dL	Any decrease – 1.5	1.6 – 2.0	2.1 – 5.0	> 5.0
WBC increase - cell/mm ³	10,901 – 15,000	15,001 – 20,000	20,001 – 25,000	> 25,000
WBC decrease - cell/mm ³	2,500 – 3,500	1,500 – 2,499	1,000 – 1,499	< 1,000
Lymphocytes decrease - cell/mm ³	750 – 1,000	500 – 749	250 – 499	< 250
Neutrophils decrease – cell/mm ³	1500-2000	1000-1,499	500-999	< 500
Eosinophils increase - cell/mm ³	650 – 1500	1501 – 5000	> 5000	Hypereosinophilic
PLT decrease - /mm ³	75,000 – 99,000	50,000 – 74,999	20,000 – 49,999	<20,000
PT – increase by factor	1.0 – 1.10 x ULN	1.11 – 1.20 x ULN	1.21 – 1.25 x ULN	> 1.25 ULN
PTT – increase by factor (partial thromboplastin time)	1.0 – 1.2 x ULN	1.21 – 1.4 x ULN	1.41 – 1.5 x ULN	> 1.5 x ULN
Fibrinogen increase - mg/dL	400-500	501-600	>600	--
Fibrinogen decrease - mg/dL	150 – 200	125 – 149	100 – 124	< 100 or associated with gross bleeding or disseminated intravascular coagulation

PLT = platelet; PT = prothrombin time; PTT = partial thromboplastin time; ULN = upper limit of normal; WBC = white blood cell count

Criteria are modified for this study based on reference values.

All graded values representing a change from baseline must be reported as AEs. For clinical or laboratory observations not addressed by the toxicity grading criteria, Grade 0= absent will be used in the AE CRF to indicate the toxicity grading criteria do not apply.

Urine	Mild (Grade 1)	Moderate (Grade 2)	Severe (Grade 3)	Potentially Life Threatening (Grade 4)
Protein	Trace	1+	2+	Hospitalization or dialysis
Glucose	Trace	1+	2+	Hospitalization for hyperglycemia
Blood (microscopic) – RBC per high power field (RBC/hpf)	1-10	11 – 50	> 50 and/or gross Blood	Hospitalization or packed red blood cells transfusion

AE = adverse event; CRF = case report form; hpf = high power field; RBC = red blood cell
Criteria are modified for this study based on reference values.
All graded values representing a change from baseline must be reported as AEs. For clinical or laboratory observations not addressed by the toxicity grading criteria, Grade 0 = absent will be used in the AE CRF to indicate the toxicity grading criteria do not apply.

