and orthostatic blood pressure and pulse rate (taken after 2 minutes in the standing position);

- Telemetry through at least 4 hours post first dose;
- Obtain fecal occult blood assessment starting approximately 6 hours post first dose on every stool sample. Stool volume and frequency will be recorded;
- Obtain occult blood on all vomitus;
- Perform brief physical examination focused on the examination of skin and oropharyngeal mucosa for evidence of bleeding and/or bruising (oral [gums] and cutaneous) 30 (+ 15) minutes after the first dose;
- Review concomitant medication usage once daily;
- Completed AE assessment (including SAEs) will be recorded on AE source forms throughout the study and placed in the subject's clinic records.

Subjects will receive standardized meals as follows on Day 1: lunch 4 hours post first dose and dinner after completion of procedures scheduled at those times; subjects will also receive a light evening snack. A drink will also be provided with each of the meals. No breakfast will be served on Day 1. Dosing will occur TID every 8 hours \pm 0.5hour.

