In addition, all AEs will be graded (Grade 1 to 4) according to the FDA Guidance for Industry: *Toxicity Grading Scale for Healthy Adult and Adolescent Volunteers Enrolled in Preventive Vaccine Clinical Trials September 2007* and the *Division of Microbiology and Infectious Diseases (DMID) Adult Toxicity Table November 2007* as modified for this study ([Appendix II](#)). For clinical or laboratory observations not addressed by the toxicity grading criteria, Grade 0=absent will be used in the AE CRF to indicate the toxicity grading criteria do not apply.

Relationship to Study Products: The PI's assessment of an AE's relationship to the study product is part of the documentation process, but it is not a factor in determining what is or is not reported in the study. If there is any doubt as to whether a clinical observation is an AE, the event will be reported. All AEs must have their relationship to study product assessed using the terms: related or not related. In a clinical trial, the study product must always be suspect. To help assess, the following guidelines will be used.

Related – There is a reasonable possibility that the study product caused the AE. Reasonable possibility means that there is evidence to suggest a causal relationship between the study product and the AE. If an alternate etiology is not identified, the AE must be considered related to study product.

Not Related – There is not a reasonable possibility that the administration of the study product caused the event.

AE's should be documented from time of dose administration through the final study visit.

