9.6 Study Halting Criteria

General:

- Any SAE
- Three or more subjects within a cohort, with the same Grade 2 event ;
- Any single Grade 3 or above finding (with the exception of aPTT as explained below);
- Evidence of hematemesis or hematochezia in 2 or more subjects
- Any other findings that, at the discretion of the PI, indicate that the study should be halted;

Electrocardiograph (ECG):

Two or more subjects within a cohort who meet any of the criteria below:

- PR: >220 ms
- QRS: >120 ms
- QTcF > 450 ms for men and >470 ms for women; or
- Change from baseline (average of pre-dose triplicate ECGs): QTcF >60 ms.

Decisions are to be based on an average QTcF value of triplicate ECGs. If an ECG demonstrates a prolonged QT interval, 2 more ECGs should be obtained over a 10 minute period. The averaged QTcF values of the 3 ECGs will then be used for decision making.

Laboratory criteria:

- Two or more subjects within a cohort have a Grade 3 increase in aPTT (confirmed on repeat) as defined by the FDA toxicity grading scale as modified for this study and as appropriate for the administration of UV-4B ([Appendix II](#)).

If any of the above events occur, the study will be halted and the SMC will review the available safety data to determine if the study should proceed as planned. If none of the events described above have been observed, dose escalation will proceed according to the protocol requirements.

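### The Appendix II diarrhea row has no count band for seven or more loose, non-watery stools, so a higher stool count can get a lower grade or none; weight and consistency are not in the scheduled stool record

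*Protocol*

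**What the plan says.** Protocol Appendix II, Systemic (General), grades diarrhea as follows:

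- Grade 1: "2 - 4 loose stools or < 400 gm/24 hours"
- Grade 2: "5-6 stools or 400 – 800 gm/24 hours"
- Grade 3: "7 or more watery stools or > 800gms/24 hours", or a need for outpatient intravenous hydration
- Grade 4: an emergency room visit or hospitalization.

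A footnote to the table adds: "All graded values representing a change from baseline must be reported as AEs". For observations that the criteria do not address, Protocol 9.2.1 says that "Grade 0=absent will be used in the AE CRF to indicate the toxicity grading criteria do not apply".

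For the stool data, Protocol 7.3.1 (Day 1) states: "Stool volume and frequency will be recorded". Sections 7.3.2 and 7.3.3 repeat this for Days 2 to 7 and Day 8, and Appendix IV has one row for it covering Days 1 to 8. No section schedules stool weight or consistency.

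The grades have direct consequences. Protocol 9.6 halts the study for "Three or more subjects within a cohort, with the same Grade 2 event", and also for one finding of Grade 3 or higher (apart from aPTT). Protocol 9.7 ends dosing for a subject with one Grade 3 AE and withdraws that subject.

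**The concern.** A grading row that feeds stopping rules should not assign a lower grade as the same kind of event gets worse. Here the qualifier on the stool count goes from loose, to none, to watery. The Grade 2 band stops at six stools and the Grade 3 count requires watery stools. A subject with seven or more loose, non-watery stools falls between them and can be graded only by weight, which the schedule does not collect.

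What is at stake is whether the numeric triggers in 9.6 and 9.7 work for this event. The three-subject rule is applied within a cohort of eight (six active, two placebo), so a single subject graded below Grade 2 can turn a count of three into a count of two. Appendix III lists diarrhea for all three marketed iminosugars, so the row is likely to be used.

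**Working it through.** The plan gives no figure to reproduce. The check applies the three cells to constructed stool records.

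**Inputs.** The Grade 1 to 3 cells of Appendix II, as quoted above.

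**Reading used.** Each "or" is a logical or, the highest matching grade is assigned, and the row is applied only when stools are loose or watery, as its label implies. The highest-grade convention is an assumption made for the check; the protocol does not state one. No record needs intravenous hydration or an emergency visit. The weights are illustrative.

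| 24-hour record | Count clause met | Weight clause met | Grade |
|---|---|---|---|
| 6 loose, 350 g | Grade 2 | Grade 1 | 2 |
| 6 loose, no weight | Grade 2 | not applicable | 2 |
| 7 loose, 350 g | none | Grade 1 | 1 |
| 8 loose, 350 g | none | Grade 1 | 1 |
| 8 loose, 600 g | none | Grade 2 | 2 |
| 8 loose, 801 g | none | Grade 3 | 3 |
| 8 loose, no weight | none | not applicable | no cell |
| 8 watery, 350 g | Grade 3 | Grade 1 | 3 |

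(Loose means loose but not watery.)

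**When the order reverses.** With weight known, seven or more loose stools grade below six only if the total is under 400 g:

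- 8 stools: 400 / 8 = 50, so a mean below 50 g per stool.
- 7 stools: 400 / 7 = 57.1, so a mean below about 57 g per stool.

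From 400 to 800 g, eight loose stools and six both receive Grade 2. Above 800 g both receive Grade 3.

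**With the scheduled data.** If volume is not converted to grams, the weight clause cannot be applied at all. Six stools are then Grade 2 and eight loose stools match no cell, whatever their size. Under 9.2.1 such a record might be entered as Grade 0. The count bands also need consistency to separate Grade 1 from no grade and Grade 3 from no grade, and consistency is not in the scheduled record either.

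**Against the triggers.** Eight loose stools under 400 g, or with no usable weight, count neither toward the three-subject Grade 2 rule nor as a Grade 3 finding under 9.6 or 9.7. Six stools do count toward the Grade 2 rule.

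**The case against.** The plan has backstops. Both 9.6 and 9.7 allow the investigator to act on other findings. The Grade 3 cell has a separate hydration clause. Appendix II also has a generic row for illness or clinical AEs, and the Safety Monitoring Committee reviews all safety data after each cohort. These stand as partial protection. But the numeric rules are there so that halting does not rest on discretion alone, and nothing says when the generic row replaces the diarrhea row.

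On data capture, the case report form is not among the documents, the AE form takes a description that could carry consistency, and volume may approximate weight. The supportable statement is therefore that only volume and frequency are scheduled, with no conversion and no consistency item specified.

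A reader might infer more than the documents support:

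- *That one normal stool is Grade 1 because it weighs under 400 g.* The row is labelled diarrhea, 9.2.1 defines an AE as an untoward occurrence, and the footnote limits reporting to changes from baseline. What remains is that the Grade 1 weight clause has no lower bound and no consistency term.
- *That six loose stools at 350 g cannot be graded.* On an ordinary reading of the alternatives they meet Grade 2. The gap is only that no rule for combining the clauses is written.
- *That the flaw distorts the primary AE tables.* Protocol 9.2.1 has the investigator rate each AE mild, moderate or severe, with the toxicity grade as an addition. SAP 10.7.2 tabulates by maximum severity, most naturally that rating. SAP 10.7.4 and 10.7.5 plan toxicity-grade summaries for laboratory values and vital signs only.
- *That diarrhea is the AE most likely to show a dose effect.* Appendix III lists signs without frequencies or dose relations for the marketed drugs, and its UV-4B findings are redacted.

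**Conclusion.** The concern holds in a limited form. The count bands leave out seven or more loose, non-watery stools. The resulting grade is below that of a six-stool record when total output is under 400 g, and there is no grade when weight is unavailable. From 400 g upward the order does not reverse. How often low-output records would occur cannot be judged from the documents. The case with no weight needs no assumption about stool size, and it is the one that the scheduled data make most relevant.

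The consequence is for the halting rules in 9.6 and the individual rule in 9.7, where a higher count of the same kind of stool can miss the numeric trigger. The conclusion assumes that the cells are applied as worded and that neither the case report form nor a manual outside these documents supplies weight, consistency or a precedence rule. It is a wording and unit inconsistency that should be corrected because it feeds stopping rules. It does not undermine the AE analysis as a whole.

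**What to change.** The sponsor should reconcile the three diarrhea cells with each other and with 9.6 and 9.7, so that more stools of the same kind cannot receive a lower grade or none. The row should also state how the count and weight clauses combine when they point to different grades. Which stool term, band limits and combining rule to use is for the sponsor to decide; none is proposed here.

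The stool log already kept on Days 1 to 8 should record what the row needs: consistency, and weight or volume in the unit that the row uses.

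The cost is revised wording in one Appendix II row and one or two fields on an existing log.
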